1. More than three doses of any opioid within one week of surgery
2. Pregnancy-
3. Prisoners
4. Unable to provide consent
5. Emergency surgery
6. Chronic kidney disease stage 5 (GFR < 15 ml/min)
7. Severe hepatic impairment
8. Recent myocardial infarction (within the last 3 months)
9. Allergy to any study related medications
10. Participation in another interventional study during the study period

3. List any restrictions on use of other drugs or treatments.

None

Statistical Considerations

a. Is stratification/randomization involved? Yes

► IF YES, describe the stratification/ randomization scheme.

- randomization will occur to either the alvimopan or placebo group after confirmation of eligibility on the day of surgery
- the randomization will be performed and the blind maintained by the Investigational Pharmacy

► IF YES, who will generate the randomization scheme?

UVA Investigational Drug Service (IDS)

2. What are the statistical considerations for the protocol?

For the purpose of the final analysis, the official clinical database will not be unblinded until medical/scientific review has been completed at the end of the entire study, protocol violators have been identified (if appropriate), and data has been declared complete.

[name] will perform the analysis for UVA

[name] will extract data from CDR. [name] works for the Department of Anesthesiology and extracts data as part of his routine job duties

Statistical Methods: For continuous variables, normality will be assessed using the Kolmogorov-Smirnov test. The Mann-Whitney U-test will be used to compare non-normally distributed data, and normally distributed data will be assessed by the Student t-test for equality of means. Categorical data will be analyzed using χ^2 or Fisher's exact test, if the count is < 5 in any cell. .

1. Time to event data (time to first bowel movement) will be analyzed using the rank-sum test.

2. visual analog scale , overall hospital charges , time to resumption of PO intake , functional outcomes QR-40 will be analyzed in the following ways:

- 11-point Numeric rating scale and QR-40 will be analyzed by way of a mixed model for repeated measures (MMRM).
- For hospital charges, either a t-test or Wilcoxon rank sum test (depending on the assessment of normality, as noted above).

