- For time to resumption of PO intake we will assume no censoring and will use the rank sum test. Finally pain scores will be calculated and displayed using summary statistics empirically without comparison testing.

All tests will be 2-sided and we will consider a P value <0.05 to be statistically significant.

3. Provide a justification for the sample size used in this protocol.

In order to power this study, we evaluated the mean time to first bowel movement at our institution, which was 3.27 days ($\sigma = 1.10$)

Based on published data 519 women undergoing gynecological surgery, we predict that perioperative alvimopan will reduce the time to first bowel movement by 30%.¹³ Assuming that the placebo group will require 3.27 days to achieve a bowel movement, that alvimopan reduces time to first bowel movement by 30% (0.98 days) without changing the standard deviation ($\sigma = 1.10$), and setting α to 0.05, power analysis suggests that we will need to randomize 42 patients in order to have a 80% chance of not making a type II error. To factor for a 10-15% dropout rate, we would recruit 60 subjects for this study.

4. What is your plan for primary variable analysis?

Time to event data (time to first bowel movement) will be analyzed using the rank-sum test.

5. What is your plan for secondary variable analysis?

visual analog scale ,overall hospital charges , time to resumption of PO intake , functional outcomes QR40 8) will be analyzed in the following ways:

- 11-point Numeric rating scale and will be analyzed by way of a mixed model for repeated measures (MMRM).
- For hospital charges, either a t-test or Wilcoxon rank sum test (depending on the assessment of normality, as noted above).
- For time to resumption of PO intake we will assume no censoring and will use the rank sum test. Finally pain scores will be calculated and displayed using summary statistics empirically without comparison testing.

6. Have you been working with a statistician in designing this protocol? Yes

[name]

7. Will data from multiple sites be combined during analysis? No

Biomedical Research

1. List the procedures, in bullet form, that will be done for RESEARCH PURPOSES as stipulated in this protocol.

- Subjects will be consented
- Prior to study randomization, subjects will undergo a physical exam and review of medical history
- All women of child bearing potential will have a urine pregnancy test performed prior to administration of study drug pre-operatively

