- Subjects will be randomized to either the alvimopan or placebo group
- Alvimopan or placebo administered orally pre-operatively
- Alvimopan or placebo administered orally or per NG twice daily post-operatively for up to seven days post-operatively, or until the time of discharge, whichever occurs first, to a maximum of 15 doses
- All intraoperative data recorded on the anesthesia record will be collected prospectively.
- BIS scores, when available, will be collected at the completion of surgery.
- Neuromonitoring data (ex. latency, amplitude, significant signal changes) will be collected at the completion of surgery.
- Postoperatively, visual analog scale (VAS) scores will be assessed daily at morning rounds.
- Additionally, nutritional intake and in hospital complications will be recorded, as will the patient's report of pain (on the 0-10 pain scale), time to first solid intake, time to first flatus and bowel movement (**primary outcome**), time to first ambulation, and consumption of all pain medications (intravenous and by mouth).
- ICU stay and hospital stay will be noted Initial post-op pain management orders will be entered by the Anesthesiologist
- to standardize opioid requirements, patients will initially be ordered hydromorphone as the intravenous opioid of choice (PCA and prn), and will only be changed (fentanyl) if specifically requested by the primary service.
- Patients will also be ordered oxycodone as the initial PO opioid of choice, and only changed to other medications (hydrocodone) if specifically requested by the primary service
- At the completion of hospitalization, QR40 will be used to assess the patients' pain and quality of life at discharge.

Total patient charges will be extracted from the University of Virginia's Clinical Data Repository.

2. Will you be using data/specimens in this study that were collected previously, with the use of a research consent form, from another research study? No

3. Will any of the procedures listed in item # 1 have the potential to identify an incidental finding? This includes ALL procedures, assessments and evaluations that are being done for RESEARCH PURPOSES that may or may not be considered investigational. No

4. Do any of the procedures listed above, under question # 1, utilize any imaging procedures for RESEARCH PURPOSES? No

5. Will you be using viable embryos? No

6. Will you be using embryonic stem cells? No

9. Are any aspects of the study kept secret from the participants? Yes

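### Does naming a repeated-measures model for a QR-40 score taken once, at discharge, leave that outcome without a workable analysis?

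*Combined protocol and SAP*

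**What the plan says.** QR-40 appears in three places in the combined protocol and SAP.

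- **Statistical Considerations, question 2, Statistical Methods, item 2.** The first bullet reads "11-point Numeric rating scale and QR-40 will be analyzed by way of a mixed model for repeated measures (MMRM").
- **Statistical Considerations, question 5 (secondary variables).** The lead-in includes "functional outcomes QR40 8) will be analyzed in the following ways". The matching bullet reads "11-point Numeric rating scale and will be analyzed by way of a mixed model for repeated measures (MMRM"), so QR-40 has gone and a loose conjunction remains. The other bullets deal with hospital charges, return to oral intake and the display of pain scores.
- **Biomedical Research, item 1 (procedures).** "At the completion of hospitalization, QR40 will be used to assess the" patients' "pain and quality of life at discharge". This is the only administration listed. Before randomisation the list has "Prior to study randomization, subjects will undergo a physical exam and review of medical history" and a pregnancy test where relevant, but no QR-40.

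The Statistical Methods text also has a general rule for continuous variables: a Kolmogorov-Smirnov check, then a Student t-test or a Mann-Whitney test. Under Hypothesis to be Tested, quality of recovery is one of three secondary objectives. The two numbered secondary hypotheses concern hospital cost and oral intake with nutrition.

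**The concern.** An MMRM is meant for outcomes measured at several visits. It estimates a within-patient covariance and uses a patient's other visits when one is missing. A single discharge score offers neither, so the named method does not match the scheduled data. Pain is different: the procedures say "visual analog scale (VAS) scores will be assessed daily at morning rounds".

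QR-40 is the only quality-of-recovery instrument in the procedures, so one secondary objective rests on it. The analysis is done by an outside statistician working from de-identified data. Read literally, the plan might leave that person with a model that cannot be fitted, or with a free choice of test after seeing the data. The silence in question 5 appears to make this worse.

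**Working it through.** **1. The plan's own figure.** No sample size or power is stated for QR-40. The only such figure is 42 patients for the primary endpoint. With a difference of 0.98 days, SD 1.10, two-sided α of 0.05, 80% power and equal arms (assumed, since no ratio is given), the exact t-test calculation gives 20.8, hence 21 per arm and 42 in total. That figure is reproduced and does not depend on how QR-40 is analysed.

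**2. What a marginal MMRM contains with one visit.** An unstructured covariance over T visits has T variances and T(T − 1)/2 covariances. For T = 1 that is 1 variance and 1 × 0/2 = 0 covariances. Visit and arm-by-visit terms drop out because there is only one visit. What remains is

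y = β₀ + β₁ × arm + error, with error variance σ²,

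and SE(β₁) = √[σ²(1/n₁ + 1/n₀)]. This is the equal-variance two-sample t-test.

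**3. Numerical check.** The data are simulated, with 30 patients per arm and one score each. They illustrate the algebra and say nothing about the trial's likely result.

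- Arm difference 5.517; residual variance 173.40.
- SE = √(173.40 × 2/30) = 3.400.
- t = 5.517/3.400 = 1.623 on 58 df, p = 0.110.
- The two-sample t-test on the same data gives t = 1.623, p = 0.110.

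A second simulated set gave t = 1.299, p = 0.199 by both routes.

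**4. If a patient random intercept is added.** Each patient has one score, so the covariance matrix is (σ²_patient + σ²_residual) × identity. Only the sum enters the likelihood. In the first data set the software put 86.70 in each part, and 86.70 + 86.70 = 173.40, the residual variance in step 3. Recomputing the arm effect by generalised least squares with 1%, 25%, 50%, 75% and 99% of that total assigned to patients gives 5.517 with SE 3.400 every time. The split is not identified; the arm comparison is.

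**5. The gap in question 5.** Its bullet matches the Statistical Methods bullet except that QR-40 is missing after the conjunction. A dropped word is the likeliest explanation. Restoring the word leads to step 2. Leaving it out leads to the general rule, which offers a t-test or a Mann-Whitney test. Both routes are two-group comparisons of the discharge score.

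**6. Missing scores.** The sample-size text says "To factor for a 10-15% dropout rate, we would recruit 60 subjects for this study". If every dropout lacked a discharge score, 60 × 0.10 = 6 to 60 × 0.15 = 9 patients would be absent from the QR-40 comparison. That would be equally true under any analysis of a single score, so it does not measure harm from naming an MMRM.

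**The case for a change.** The best case for a change is that a plan should name the analysis that will actually be run, and the correction is a few words. Three parts of that case deserve an answer.

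*A literal fit can mislead.* This is partly true. In step 4 the random-intercept software fit reported an SE of 2.972 and p = 0.063, against the correct 3.400 and p = 0.110. It did so with a warning that the Hessian was not positive definite, so the printed SE is a numerical artefact. A marginal MMRM has no random intercept and does not meet this problem, and a trial statistician would not report a fit carrying that warning with one row per patient. It is a reason for care in fitting, not a defect in the plan's comparison.

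*The choice of test is left open.* If the discharge scores look non-normal, the MMRM bullet leads to a t-test while the general rule would lead to Mann-Whitney. That small freedom stands. The documents give no QR-40 distribution, so its effect cannot be sized. The specific instruction ordinarily takes precedence over the general one, and the plan keeps the database blinded until the data are declared complete, so the choice can be settled before then. Objecting to a test chosen after a normality check is a separate criticism that applies equally to hospital charges.

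*Repeat QR-40 assessments may have been intended.* The documents do not exclude this, but none is scheduled, and the procedures describe the score as status at discharge. On the schedule as written, the two-group comparison is the only one available.

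The contrast with pain is also less tidy than it looks. Daily scoring is stated for the VAS, whereas the MMRM bullet names the 11-point scale, and the same lists say pain scores will be summarised without a formal comparison. That is a separate inconsistency and does not affect QR-40.

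**Conclusion.** The concern describes the text correctly but does not call for a change. The named model reduces to the two-sample comparison that would replace it, with the same estimate, standard error and p-value, so a rewrite would gain nothing in the result. The omission in question 5 is most likely clerical, and the general rule for continuous variables covers it. Reporting the day of assessment by arm, or fixing a rank test in advance, would be matters of preference.

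This rests on three assumptions: QR-40 is scored once, at discharge, as the procedures say; the model is fitted in its marginal form or collapsed to arm only; and the result is read as status at discharge, not recovery at a common post-operative day. Only a secondary objective is touched. The primary endpoint and the figure of 42 are unaffected.

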Pre-screening for IRB purposes is the term used to describe activities PRIOR to obtaining Informed Consent and may not include any research procedures.

The activities may involve pre-screening of potential subjects over the telephone or in person is generally performed to determine their initial eligibility for, and, interest in a study and is a common strategy in the recruitment process.

Questions appropriate for pre-screening address the specific inclusion/exclusion criteria for the study and other issues of suitability, for example, an individual's ability to come to the research site multiple times.

It is not appropriate at this point in the process (i.e. prior to obtaining informed consent/enrollment) to gather information that is not directly related to assessing eligibility and suitability (e.g. obtaining complete medical histories, obtaining blood specimens for lab tests). An additional telephone script is not required, for this pre-screening process, in addition to any scripts required under Recruitment question # 2.

Answer/Response: Yes “What do you use for pain control and how often do you take it?” is the only pre-screening question that will be asked.

IF YES, submit any documents that will be used to collect pre-screening information so that the IRB may confirm what questions will be asked.

NOTE: To comply with HIPAA regulations only the minimum necessary information may be collected at this time. This means that only questions pertaining to the Inclusion and Exclusion Criteria may be asked.

IF YES,

DHHS: study team requests a Waiver of Documentation of Consent for Pre-screening questions.

HIPPA:

HIPAA does not apply if:

--no PHI is collected or

--if PHI is collected from a potential subject by an individual from a department that is not part of the HIPAA covered entity.

HIPAA does apply if the collection occurs by individuals* who work in a department that is part of the HIPAA covered entity.

In this case the collection will be covered under Health Care Operations/

These individuals are those that meet one of the following criteria:

--a UVa student working in the UVa HIPAA Covered Entity*

--a faculty or staff member in a PAID appointment in the UVA HIPAA Covered Entity*

IF YES, Will any of the questions involve health information?

Answer/Response: “What do you use for pain control and how often do you take it?” is the only pre-screening question that will be asked.

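### No pain score is scheduled before the first dose, so the planned pain MMRM cannot adjust for pre-operative pain: an inexpensive gain in precision is missed

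*Combined protocol and SAP*

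**What the plan says.** Pain scores and quality of recovery are listed under the secondary objective (Hypothesis to be Tested).

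**Collection (Biomedical Research, item 1).** The visual analogue score is placed after surgery: "Postoperatively, visual analog scale (VAS) scores will be assessed daily at morning rounds". The next bullet adds the 0-10 report, "as will the patient's report of pain (on the 0-10 pain scale"), among other post-operative recordings, with no time point of its own. QR-40 is given once: "At the completion of hospitalization, QR40 will be used to assess the patients' pain and quality of life at discharge". Before allocation the list has consent, a pregnancy test where applicable, and this: "Prior to study randomization, subjects will undergo a physical exam and review of medical history". The only pre-screening question is "What do you use for pain control and how often do you take it" (Appendix: Recruitment, item 3).

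**Analysis (Statistical Considerations, item 2).** "11-point Numeric rating scale and QR-40 will be analyzed by way of a mixed model for repeated measures (MMRM"). Item 5 repeats the model for the 11-point scale. Neither item names a covariate. Both also end with a sentence that points the other way: "Finally pain scores will be calculated and displayed using summary statistics empirically without comparison testing".

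**Allocation (Statistical Considerations).** "randomization will occur to either the alvimopan or placebo group after confirmation of eligibility on the day of surgery". No stratification factor or allocation ratio is given.

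**The concern.** Patients who come to major spine surgery can be expected to differ in how much pain they already have, and that pain may predict their scores afterwards. A model for post-operative pain usually uses such a baseline to remove between-patient variation. Here there is no baseline to use. It cannot be collected later, because the first dose is given on the day of surgery before the operation starts (Appendix: Pharmacy-Approved Drug, item 9).

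The Background gives the outcome some weight. It criticises earlier trials of the drug for inferring analgesia from opioid consumption without measuring pain control. If the useful result here is that pain is not made worse, the width of the confidence interval decides how much can be said, and a baseline covariate can narrow that interval.

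**Working it through.** **1. What is recorded before the first dose.** Going through the research procedures and appendices:

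- Physical examination and medical history: no pain score listed.
- Pre-screening question: analgesic type and frequency, not intensity.
- Clinical Data Repository extract: only the financial category is marked.
- VAS: post-operative by its own wording.
- 0-10 report: timing not stated; its place in the post-operative list is the only indication.
- QR-40: discharge only.

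So no score on the outcome scale is scheduled before treatment.

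**2. The plan's own figure.** There is none for pain. The stated sample size (item 3) is for the primary endpoint: standardised effect 0.981/1.10 = 0.892, two-sided alpha 0.05, power 80%. The exact two-sample t-test needs 20.74 per arm, hence 21 per arm and 42 in total, as stated. I use 42 and the 60 to be recruited as the range of patients analysed, with 1:1 allocation assumed.

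**3. Size of a chance imbalance.** In units of the patient SD, the difference in mean pre-operative pain has standard deviation s = sqrt(2/n), with n per arm.

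- n = 21: s = sqrt(2/21) = 0.309. P(|difference| > 0.25) = 2[1 − Φ(0.25/0.309)] = 42%; above 0.5 it is 11%.
- n = 30: s = sqrt(2/30) = 0.258. The same probabilities are 33% and 5%.

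**4. Precision given up.** At one time point, adjusting for a baseline with correlation r multiplies the variance by 1 − r². The difference detectable with 80% power is (1.96 + 0.8416) × s unadjusted, and that times sqrt(1 − r²) adjusted. The documents do not give r; the values below are assumptions.

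| r | Variance reduction | Detectable difference, 42 analysed (unadjusted 0.86 SD) | Detectable difference, 60 analysed (unadjusted 0.72 SD) |
|---|---|---|---|
| 0.2 | 4% | 0.85 | 0.71 |
| 0.3 | 9% | 0.82 | 0.69 |
| 0.5 | 25% | 0.75 | 0.63 |
| 0.6 | 36% | 0.69 | 0.58 |

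**5. What a given imbalance does to the unadjusted test.** With no treatment effect and an imbalance x, the post-operative difference has mean r·x and standard deviation s·sqrt(1 − r²). The unadjusted test rejects when the difference exceeds 1.96·s in absolute value. Example with n = 30, r = 0.5, x = 0.5: mean 0.25, standard deviation 0.258 × 0.866 = 0.224, limit 1.96 × 0.258 = 0.506. The upper tail beyond (0.506 − 0.25)/0.224 = 1.15 plus a negligible lower tail gives 13%.

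For r from 0.3 to 0.6:

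- x = 0.25 SD: shift 0.075 to 0.15 SD; conditional false-positive rate 4.3-4.9% (n = 30) or 3.4-4.6% (n = 21), so not inflated.
- x = 0.5 SD: shift 0.15 to 0.30 SD; conditional rate 8-16% (n = 30) or 7-11% (n = 21).

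**The case against.** The strongest reply is that randomisation already protects the comparison. This stands. Allocation is randomised and double-blind, the unadjusted estimate is unbiased on average, its overall type I error is 5%, and its interval already allows for chance differences at baseline. A reader might infer that a pain difference in this trial could not be told apart from one that existed before surgery, or that a harmful imbalance is likely. The documents support neither. The commoner imbalance, 0.25 SD, does not raise the false-positive rate in step 5. The one that does, above 0.5 SD, has a probability of 5-11%.

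The gain also depends on a correlation that no document reports. At 0.2 to 0.3 it is 4-9% of the variance. The factor 1 − r² is a single-time-point result and was not derived for the daily repeated-measures model. This stands too, and it limits the claim to a modest one.

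The plan says both that the 11-point scale goes into an MMRM and that pain scores are shown without testing. If the second statement governs, there is no model to adjust. That makes reconciling the two part of the fix. A baseline score by arm would still help a reader of a purely descriptive display.

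The sentence that places scoring after surgery concerns the VAS, whereas the model is for the 11-point scale. This is fair, but the 0-10 report has no pre-operative time point either. History and analgesic use give indirect information on earlier pain. They are not scores on the outcome scale, and the plan does not name them for the analysis. The opioid exclusion limits recent doses and does not measure pain.

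**Conclusion.** The point holds as an inexpensive improvement to a secondary outcome. No pre-treatment pain score is scheduled, so the planned pain model cannot use one. The cost is precision and protection against a chance imbalance in this one trial. Neither the validity of the randomised comparison nor its overall error rate is affected.

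The single-time-point variance forgone is 4% to 36% for an assumed correlation of 0.2 to 0.6. The imbalance probabilities rest on 1:1 allocation and 42 to 60 patients analysed. The primary analysis and its 42 patients do not depend on any of this. It should be settled before enrolment, because a missed baseline cannot be recovered after the first dose.

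**What to change.** - **Biomedical Research, item 1:** add that the 0-10 pain score is recorded at the pre-randomisation examination, before the first dose, on the same named scale as the post-operative score.
- **Statistical Considerations, items 2 and 5:** state that the MMRM for that scale includes the pre-operative score as a covariate and, if the sample supports it, its interaction with day.
- **Same edit:** reconcile the MMRM lines with the sentence that pain scores are displayed without comparison testing. If pain is only described, report the baseline score by arm.

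The cost is one question per patient, plus one model parameter, or a few if the interaction with categorical day is included. A pre-operative QR-40 is optional, would add a questionnaire, and is not needed for this point.

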An emerging body of data suggests that intraoperative opiate use results in increased post-operative opiate requirements²⁻⁴ although this is controversial.⁵⁻⁷ Because of the side effects associated with opioid use, much effort has been devoted to the development of alternative and/or complementary analgesic regimens. Unfortunately, in early 2009 much of the promising data on alternative/complementary analgesic modalities was shown to have been fabricated. In all, twenty-one peer-reviewed papers in support of ketorolac, COX-2 inhibitors (celecoxib, rofecoxib, and valdecoxib), clonidine, verapamil, venlafaxine, pregabalin, and gabapentin were retracted. Thus, the goal of achieving improved perioperative pain control is as important, and distant, as ever

Alvimopan is a peripheral-acting opiate antagonist designed to decrease the gastrointestinal complications of perioperative systemic opioid administration. It has been studied in 11 randomized, controlled trials encompassing 4175 patients over the course of seven years. In all but one study, bowel recovery was improved following alvimopan administration, and in all but two, post-operative analgesia was reportedly unaffected

Despite existence of a large, growing body of literature supporting the use of alvimopan, further analysis is warranted for several reasons. First, and foremost, all eleven randomized trials of alvimopan were conducted using in patients undergoing intraabdominal surgery. While these patients universally suffer from post-operative ileus (because of proximity between the site of surgery to the GI tract), other patient populations (such as major spine surgery patients) also suffer from post-operative ileus

Second, the vast majority of data on alvimopan assesses effective analgesia by comparing morphine equivalents between groups (the implication being that if morphine equivalents are equal, no inhibition of analgesic effect has occurred). This methodology does not actually assess pain control or patient satisfaction

Third, several studies have shown an improvement in time to discharge or discharge order⁸⁻¹², without examining whether or not the difference in time to discharge translated into a reduction in hospital charges. Bell et al. pooled data from several alvimopan trials and estimated that mean hospital costs were reduced between \$879 and \$977 per patient, although this analysis was not based on the neurosurgical patient population.⁸

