Lastly, the primary outcome in all eleven randomized, clinical trials is some variation of return of GI function. Patients who undergo reconstructive spinal procedures offer an additional clinical outcomes – functional status and postoperative satisfaction (as measured by the Oswestry Disability Index [ODI], the short form 12, and the short form 36 scores)

Hypothesis to be Tested

Primary Objective: examine the impact of alvimopan on time to first bowel movement in patients who undergo major spinal surgery

Primary Hypothesis: the perioperative use of alvimopan in major spine surgery reduces the time to first bowel movement

Secondary Objective: examine the impact of alvimopan on:

- overall hospital cost
- quality of recovery
- pain scores

Secondary Hypotheses: the perioperative use of alvimopan in major spine surgery

- 1) reduces overall hospital cost [even when taking into account the cost of the drug]
- 2) results in earlier resumption of full PO intake and consequently improved post-operative nutrition

Study Design: Biomedical

1. Will controls be used? Yes

► IF YES, explain the kind of controls to be used. placebo controlled study

7. What is the study design?

Randomized, Double-Blind, Placebo-Controlled Trial

8. Does the study involve a placebo? Yes

► IF YES, provide a justification for the use of a placebo

Compelling methodological reasons for use of placebo;
Participants are not deprived of interventions they would otherwise receive; *and*
Research intended to develop interventions that will benefit the host population.

Human Participants

1. How many subjects will sign a consent form under this UVA protocol? 60

2. Provide an estimated time line for the study. 100% enrolled in 2 years

Inclusion/Exclusion Criteria

INSTRUCTIONS:

The inclusion and exclusion criteria should be written in bullet format.

If this is a collection of only retrospective* specimens or data, the inclusion criteria must include a start and stop date for when specimens/ data will be collected.

The stop date must be prior to the version date of this protocol.

*Retrospective: all specimens are in a lab at the time this protocol is approved by the IRB. All data exists in medical records or records from previous studies at the time this protocol is approved by the IRB.

1. List the criteria for inclusion

1. Major spine surgery scheduled as part of clinical care
2. 18-80 years

2. List the criteria for exclusion

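### Secondary hypothesis 1 (hospital cost) rests on an unadjusted test of total charges; a mean difference with a 95% CI, adjusted for the extent of the operation, would be more precise and answer the cost question directly

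*Combined protocol and SAP*

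**What the plan says.** - **Hypothesis.** Under Hypothesis to be Tested, secondary hypothesis 1 is that alvimopan "reduces overall hospital cost [even when taking into account the cost of the drug".
- **Variable.** Biomedical Research, item 1: "Total patient charges will be extracted" from the Clinical Data Repository. No charge component is excluded and no time window is set.
- **Test.** Statistical Considerations, items 2 and 5: "For hospital charges, either a t-test or Wilcoxon rank sum test (depending on the assessment of normality, as noted above". No covariate is named, no stratification factor is described, and no effect estimate or confidence interval is requested.
- **Case mix.** Eligibility is scheduled major spine surgery at ages 18 to 80, with no limit on type or extent.
- **Size.** The sample size (42 needed, 60 recruited) rests only on time to first bowel movement. No mean, SD, effect or power is given for charges.
- **Background figure.** A pooled analysis of alvimopan trials "estimated that mean hospital costs were reduced between" $879 and $977 per patient, "although this analysis was not based on the neurosurgical patient population".

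**The concern.** Total charges for a spine operation, read plainly, include theatre time, implants and anaesthesia. The documents do not itemise them, so this is an inference, but nothing in the plan takes them out. Randomisation precedes surgery and the trial is double-blind, so these charges should be equal in expectation between arms; a peripherally acting opioid antagonist has no evident route to change them. In an unadjusted comparison they widen the error and contribute nothing to the difference sought. With an unrestricted case mix, that extra variance could be large.

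The second problem is the quantity reported. A cost claim concerns the mean amount per patient. If charges fail the normality check, the planned result is a rank-sum P value, which gives no mean difference in dollars.

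At stake is how the result is read. An imprecise, non-significant comparison, reported only as a P value, could be taken to show that the drug saves nothing.

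**Working it through.** **1. Reproduce the plan's own figure.** Inputs from Statistical Considerations, item 3: difference 0.98 days, SD 1.10, two-sided 0.05, power 80%. The noncentral-t calculation gives 20.8, so 21 per arm and 42 in total, as stated. The same method is used below for charges.

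**2. Inputs for charges.** From the documents: 60 recruited, two-sided 0.05. Assumed: 1:1 allocation, so 30 per arm. For scale only: $879 and $977. The SD of charges is not in the documents and is varied.

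**3. Largest SD that gives 80% power.** At 30 per arm the detectable standardised difference is 0.7356.
- 879 / 0.7356 = $1,195
- 977 / 0.7356 = $1,328

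At 21 per arm it is 0.886, and the limits are $992 and $1,103.

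**4. Power and precision over assumed SDs, 30 per arm.** Noncentrality = (difference / SD) × √(30/2). For example, (879 / 5,000) × 3.873 = 0.681, which gives 10.3% power. The 95% CI half-width is about 1.96 × SD × √(2/30) = 0.506 × SD.

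| Assumed SD | Power, $879 | Power, $977 | 95% CI half-width |
|---|---|---|---|
| $1,000 | 92% | 96% | $506 |
| $2,000 | 39% | 46% | $1,012 |
| $5,000 | 10% | 12% | $2,530 |
| $10,000 | 6% | 7% | $5,061 |
| $20,000 | 5% | 5% | $10,121 |

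These figures are for the t-test; the rank-sum alternative was not computed.

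**5. What adjustment buys.** If a share f of the variance is explained by the operation, the standard error is multiplied by √(1 − f). The share is an assumption.
- f = 0.5: √0.5 = 0.71, a fall of 29%
- f = 0.8: √0.2 = 0.45, a fall of 55%

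Power for $879 / $977 after adjustment:

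| Assumed total SD | f = 0.5 | f = 0.8 |
|---|---|---|
| $5,000 | 16% / 18% | 32% / 38% |
| $10,000 | 8% / 8% | 12% / 13% |
| $20,000 | 6% / 6% | 7% / 7% |

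At SD $10,000 with f = 0.8, the CI half-width falls from $5,061 to 5,061 × 0.447 = about $2,260. That is a real gain in precision, but the comparison is still far from 80% power for a difference of this size.

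**The case against.** A reader might infer that noise from surgery swamps the cited saving and that the test is uninformative whatever the truth. The documents do not support that. They give neither an SD for charges nor the share due to the operation; stay, ICU time and complications vary too. A true difference of 0.74 SD or more would have at least 80% power at 30 per arm.

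The benchmark is also weak. The $879 to $977 is a saving in costs, the tested variable is charges, and the protocol itself says the population differed. It is background and was never used to size the trial. Low power for a secondary outcome that was not powered is common and not in itself an error. This stands, so the figure serves here only to show scale. If charges ran at four times cost (an assumption), power at SD $20,000 would be 10-12%.

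It is tempting to test only charges after surgery, or total minus theatre, implant and anaesthesia charges. These are different variables, and neither is equivalent to covariate adjustment. Either would replace the stated outcome, overall cost, with a narrower one. Randomisation and the first dose both come before the operation, so day-of-surgery charges arise after randomisation. That objection stands, and the total should remain the tested outcome.

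A reader might also infer that stay is never compared, since the plan says only that "ICU stay and hospital stay will be noted". The general rule for continuous variables in item 2 can already cover it, so no new tested outcome is needed.

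Finally, the hypothesis is about cost net of the drug, while the variable is charges and the manufacturer supplies the study drug (Support Source appendix). Adjustment does not resolve that difference.

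**Conclusion.** The point holds as an inexpensive improvement to a secondary analysis; it does not touch the primary outcome. Two parts do not depend on any assumed SD: charges driven by the operation add variance without expected signal, given that the drug does not alter the operation, and a rank-sum P value does not estimate the mean difference that a cost claim needs.

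The size is conditional. A difference of $879 to $977 is testable with 80% power at 30 per arm only if the SD is at most about $1,195 to $1,328. At assumed SDs of $5,000 and $10,000, power is 10-12% and 6-7%. Adjustment cuts the standard error by 29-55% if 50-80% of the variance is operative. It does not by itself make the comparison well powered, so the interval and how it will be read matter as much as the adjustment.

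**What to change.** In Statistical Considerations, items 2 and 5:

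1. Keep total patient charges as the tested outcome.
2. Report the difference in mean charges between arms with a 95% CI, by bootstrap for example if charges are skewed, from a model adjusted for the extent of the operation. Prefer a measure fixed before randomisation, such as the scheduled procedure, and name it before unblinding.
3. If the extract can be itemised, show charges excluding theatre, implants and anaesthesia as a supportive analysis, and note that the excluded items arise after randomisation.
4. State that a non-significant result will be interpreted from the CI and not taken as evidence of no saving.

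The cost is slightly more analysis work and a check that the extract can be itemised; the Clinical Data Repository appendix marks only the financial category and does not show the level of detail. If it cannot be itemised, step 3 is dropped and the rest is unaffected.
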